1 SYNOPSIS

Name of Sponsor/Company: Galera Therapeutics, Inc.	
Name of Investigational Product: GC4711	
Title of Study: Phase I/II, Randomized, Placebo-Controlled Study of Stereotactic Body Radiation Therapy (SBRT) and GC4711 for Centrally Located or Large, Node-Negative Non-Small Cell Lung Cancer (NSCLC)	
Number of Study Center(s): Phase 1: Approximately 4 centers in the United States Phase 2: Up to 20 centers in the United States	
Estimated Enrollment Period: ~36 months	
Studied period (years): First patient enrolled, Phase 1: Q4 2020 Last patient completed, Phase 1: Q3 2021 First patient enrolled, Phase 2: Q3 2021 Estimated date last patient completed, Phase 2: Q3 2023	Phase of development: 1-2
Objectives: Phase I Primary: To assess the safety of GC4711 administered intravenously (IV) in combination with 5 fractions of stereotactic body radiation therapy (SBRT) in subjects with Non-Small Cell Lung Cancer (NSCLC) Secondary: To evaluate the efficacy, and acute and late toxicities of GC4711 + 3 or 5 fractions of SBRT	
Objectives: Phase II Primary: To determine the percentage of patients with complete or partial in-field tumor response based on the RECIST 1.1 criteria through 6 months following completion of SBRT Secondary: 
• To determine the best in-field tumor response at 6-, 12-, 18- and 24-months following completion of SBRT• To compare progression-free survival, overall survival, local tumor control, and distant metastasis rates over a 2-year follow up period for SBRT plus GC4711 or placebo• To assess durability of in-field complete or partial responses• To determine acute lung toxicity after SBRT + GC4711 compared to SBRT + placebo for early-stage NSCLC• To evaluate the rate of acute and late radiation toxicities for SBRT + GC4711 compared to SBRT + placebo	

- To assess the relationship between clinical, functional and radiographical lung function changes observed after SBRT

Exploratory (Phase I and II)

- To evaluate risk of lung injury, its development pattern over time, and patient/disease and dosimetry characteristics in relation to additional GC4711
- To evaluate the pharmacokinetics of GC4711 in the study population
- To collect initial information about acute effects of GC4711, including cardiovascular events and electrocardiogram parameters

Rationale:

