The primary endpoint will be the difference in in-field RECIST response rate at 6 months post SBRT completion.

The secondary endpoints will include overall response, pulmonary function, pneumonitis assessed clinically and radiographically, and time to event endpoints (PFS, OS, Local and Distant Control).

Detailed information on dose-volume exposure, co-treatment and sensitivity profiles of existing obstructive lung disease will be collected for pneumonitis-risk analyses. Pharmacokinetic (PK) sampling and cardiac monitoring will be performed on each subject with two separate doses of GC4711 (or placebo) collecting blood samples pre-infusion and post-infusion for each.

Number of Subjects:

Phase 1: 5 subjects

Phase 2: Approximately 66 subjects (~33 per arm, GC4711 or placebo)

Diagnosis and Main Criteria for Inclusion:

Inclusion Criteria:

1. Male or female subjects at least 18 years of age.
2. Ability to understand and the willingness to sign a written informed consent.

3. Histological or biopsy proven Non-Small Cell Lung Cancer. For peripheral lesions, cytology and/or clear imaging-guided suspicion is accepted if histology cannot be obtained.
4. ECOG performance status of 0-3.
5. Node negative (T1 to T3N0M0), centrally located (within 2cm in all directions around the proximal bronchial tree, including ultra-central tumors, abutting the bronchial tree or trachea) or large (>1-7cm) Non-Small Cell Lung Cancer (NSCLC), judged acceptable for SBRT by the treating Investigator. Staged with FDG-PET/CT, brain CT or MRI with contrast and/or mediastinoscopy, measurable disease as defined by RECIST 1.1.
6. Adequate end-organ function, based on routine clinical and laboratory workup:
 - a. ANC >1,000 cells/ μ l, Platelets \geq 75,000 cells/ μ l, Hemoglobin \geq 7.0 g/dl
 - b. Serum creatinine \leq 2 mg/dL or calculated creatinine clearance \geq 30 ml/min
 - c. Total bilirubin \leq 1.5 x ULN (or direct bilirubin below the ULN), AST and ALT \leq 2.5 x ULN
7. Males and females of must agree to use effective contraception starting prior to the first day of treatment and continuing after the last dose of GC4711/Placebo for 30 days (females) and 90 days (males).

Exclusion Criteria

1. Subjects with confirmed nodal and/or distant disease (including brain) using standard workup (per investigator).
2. Subjects with peripheral lesions of 1cm or smaller
3. Prior treatment with immunotherapy within 3 months prior to Day 1 dosing.

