4.2 Study Duration for Participants

The study duration for participants is expected to be approximately 25 months. This includes a 21-day screening period, a treatment period of approximately 5-10 days, and long-term follow-up for 24 months. All subjects are evaluated 30 days after SBRT and 6, 12, 18 and 24 months post-SBRT.

If a participant experiences progressive disease prior to 24 months post-SBRT completion, they will continue for survival follow-up until end of study (24 months following the last administration of SBRT). No additional tumor assessments will be required after progression; however, adverse events for long term radiation toxicities will continue through 12 months post SBRT completion and survival follow up will continue through 24 months post SBRT completion.

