8.5 Statistical Analyses

The statistical analysis plan will be finalized prior to database lock and will include a more detailed description of the statistical analyses described in this section. Should the statistical analysis plan and the protocol differ with respect to analytic conventions, the statistical analysis plan supersedes the protocol. Given the study has not been powered for formal hypotheses testing, all P-values should be considered descriptive in nature. As such no alpha adjustment for multiple testing is planned.

All time to event endpoints will be measured from date registration (Phase 1) or randomization (Phase 2).

Primary Endpoints:

Phase 1: DLT defined in Section 7.5.

Phase 2: The difference in in-field tumor response between GC4711 and placebo through Month 6 following SBRT will be estimated, and a two-sided 90% confidence interval constructed around the difference using the large sample confidence interval with limits $\pm Z.05 \sqrt{[(p1*(1-p1)/n + p2*(1-p2)/m)]}$ of the point estimate where p1 and p2 are the response rates and n and m the corresponding number of patients in each arm. In addition, a Fisher's Exact test will be performed but should be considered descriptive in nature. Phase 2: Percent reduction of in-field tumor response at Month 6 compared to baseline.

Secondary Efficacy Endpoints:

Phase 1: All Phase 1 efficacy endpoints will be summarized descriptively.

Phase 2: Response rate (PR+CR at any time during the study) per RECIST 1.1 will be compared using the same methodology as the primary endpoint.

In-field tumor response at Months 6, 12, 18 and 24 will be compared for the two treatment arms using a t-test at each timepoint and corresponding two-sided 90% confidence intervals constructed about the difference. The maximum reduction for each patient observed at any time will be analyzed similarly.

Progression-free survival (PFS) will be compared using a hazard ratio along with the associated 2-sided 90% confidence interval, using an un-stratified Cox's proportional hazard model and further characterized by Kaplan-Meier curves as well as the median and survival probability at

representative times (e.g. at 2, 4, 6, 4 etc. months). A log-rank test comparing treatment arms based on the score statistic from the Cox regression will also be provided. Patients who have not progressed or died will be censored at their last evaluable response assessment.

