Overall Survival (OS) as well as duration of local and regional control will be analyzed using the same approach as PFS. For OS, patients who have not died as of the time of analysis will be censored the date last known to be alive. For duration of local and regional control, local enlargement, marginal failures, involved lobe failure, or local relapse will be considered failure events for local control. Regional failure with nodal progression (new lesions) in the mediastinum will be a failure event for regional control. Distant metastases from the index lung cancer or a second primary tumor are not considered local progression. Patients who die with lung cancer, but who do not have documented local progression will be considered non-failures for local progression and will be censored on the day of their death. Patients who die without progressive lung disease and have no documented local progression will be considered non-failures for local progression and will be censored on the day of death.

Distant-metastases rate will be summarized descriptively.

Exploratory Endpoints

All safety endpoints will be summarized descriptively including mean and mean change from baseline for continuous endpoints and n and percent for categorical endpoints.

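### Local and regional control is read from Kaplan-Meier curves with deaths censored, which overstates 2-year failure, and distant metastasis has no between-arm estimate

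*Combined protocol and SAP*

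**What the plan says.** The Phase 2 secondary objective in the Synopsis is "To compare progression-free survival, overall survival, local tumor control, and distant metastasis rates over a 2-year follow up period", and section 3 repeats it. The Synopsis methodology lists the secondary endpoints as including "time to event endpoints (PFS, OS, Local and Distant Control").

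Section 8.5 then treats the endpoints differently.

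- **Local and regional control:** "Overall Survival (OS) as well as duration of local and regional control will be analyzed using the same approach as PFS". For PFS that means a hazard ratio with a two-sided 90% interval "using an un-stratified Cox's proportional hazard model and further characterized by Kaplan-Meier curves", plus the median, survival probabilities at chosen times and a log-rank test. Patients who die without documented local progression are censored at death, whether or not they die with lung cancer. For the second group the text is that those who "have no documented local progression will be considered non-failures for local progression and will be censored on the day of death".
- **Distant metastasis:** "Distant-metastases rate will be summarized descriptively". Section 7.1 defines the term anatomically. It gives no time origin, denominator, or rule for death and incomplete follow-up.

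On imaging, section 4.2 states: "No additional tumor assessments will be required after progression". PFS is censored at the last evaluable assessment, whereas local control runs to the day of death. Section 8.5 names no competing-risk estimator for any endpoint.

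**The concern.** A patient who dies without local failure can no longer have one. Kaplan-Meier with deaths censored behaves as if such patients remained at the same risk as survivors. Its complement therefore describes a world without death and is too high as the proportion of patients who fail by 2 years. This population has substantial mortality: the protocol's own benchmark is about 30% dead at 2 years.

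For distant metastasis the problem is an omission. The objective promises a comparison and the analysis section supplies none, although PFS, OS and local and regional control each get a between-arm estimate with a 90% interval.

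Section 8.1 justifies the trial's size partly by the efficacy data it will give for planning later studies. Two-year failure proportions by arm are the figures such planning uses. As written, one set would be biased upward and the other would have no stated comparison.

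**Working it through.** **Inputs from the documents.** Two-year local control about 90% and overall survival about 70% (Synopsis rationale; section 2.1). Control about 70% in other studies (section 2.1). Sixty-six randomised 1:1, so about 33 per arm, for 60 evaluable (section 8.1).

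**Assumptions.** Hazards are constant over 2 years. The quoted control rates are treated as Kaplan-Meier estimates with deaths censored. Competing death D is 30%, from 1 − 0.70. This treats every death as occurring before local failure, so a range of 10% to 40% is shown.

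**The plan's own figures.** 1.645 × √(0.25/30 + 0.25/30) = 0.212, matching the stated 21.2%. 60/0.91 = 65.9, matching 66. No event count or precision is stated for local, regional or distant failure.

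**Step 1: size of the overstatement.** Let F be one minus Kaplan-Meier at 2 years, hL = −ln(1 − F) and hD = −ln(1 − D). Then

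cumulative incidence = hL/(hL + hD) × [1 − (1 − F)(1 − D)].

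- F = 0.10, D = 0.30: 0.1054/(0.1054 + 0.3567) × (1 − 0.63) = 0.2280 × 0.37 = 8.4%.
- F = 0.30, D = 0.30: 0.5 × (1 − 0.49) = 25.5%.

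| Competing death | F = 10% | Excess (points) | F = 30% | Excess (points) |
|---|---|---|---|---|
| 10% | 9.5% | 0.5 | 28.6% | 1.4 |
| 20% | 9.0% | 1.0 | 27.1% | 2.9 |
| 30% | 8.4% | 1.6 | 25.5% | 4.5 |
| 40% | 7.9% | 2.1 | 23.9% | 6.2 |

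A simulation of 400,000 patients at D = 30% gave 10.0% against 8.5%, and 30.0% against 25.5%. In an arm of 33, the 30% row is a gap of about 0.5 patient (33 × 0.016) or 1.5 patients (33 × 0.045).

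**Step 2: what the hazard ratio does and does not compare.** Suppose the local-failure hazards are equal but competing death is 20% in one arm and 30% in the other. Kaplan-Meier is then identical in both arms and the hazard ratio is 1. Cumulative incidence is 9.0% against 8.4% (F = 10%), or 27.1% against 25.5% (F = 30%). Both statements are true; they answer different questions.

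**Step 3: bias against sampling error.** The 90% half-width for an arm difference with 33 per arm is 1.645 × √(2p(1 − p)/33). It is 11 points at p = 8.4% and 18 points at p = 25.5%, against biases of 1.6 and 4.5 points.

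**Step 4: number of events.** Expected local failures are 66 × 0.0844 = 5.6, or 66 × 0.255 = 16.8. The 90% interval for the hazard ratio is the estimate multiplied or divided by exp(1.645 × 2/√6) = 3.8 with 6 events, or 2.2 with 17. The chance that at least one arm has no event:

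- At 8.4%: 0.9156^33 = 5.4% per arm, so 11% with equal arms. It is 28% if GC4711 is assumed to halve the rate (0.9578^33 = 24.1% in that arm).
- At 25.5%: 0.01% with equal arms, 1.1% if halved.

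**Step 5: distant metastasis when imaging may stop.** An illustrative simulation of 2 million patients per arm used visits every 6 months. It assumed 20% metastasis at 2 years, local failure 15% against 30%, and a metastasis hazard doubled after local failure. The true difference of about −1.0 point, in favour of the arm with better local control, appears as about +0.6 if metastases are counted only up to first progression. All these inputs are assumed; the result shows direction only. An analysis of metastasis as first progression, with other-site progression competing, counts the same events and gives the same +0.6.

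**The case against.** The strongest reply is that the plan's comparison of local control is sound. Cox and log-rank analyses with deaths censored validly compare cause-specific hazards, and the objective speaks of local tumor control, not cumulative failure. That stands. A reader might infer that the plan cannot validly compare local and regional control; the documents do not support this. What the plan lacks is a valid estimate of the proportion failing by 2 years.

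The bias is also modest. It is well below the sampling error, much of it would cancel between arms with similar mortality, and setting D to all-cause mortality counts some deaths that follow local failure. That stands too, and is why a range is given.

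A reader might further infer that the hazard ratio will often be inestimable. That is a real risk only at 90% control. At 70% control an arm with no events is very unlikely, and section 2.1 says the trial targets tumors at higher risk of local failure.

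Censoring at death instead of at the last scan matters little between scheduled visits, because failures are found at scans. It matters for unscanned time after another type of progression. A simulation of that effect gave only 0.1 to 0.2 points, in the downward direction. Section 4.2 makes such scans optional; it does not forbid them.

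Finally, section 8.5 declares P-values descriptive and leaves detail to an analysis plan that takes precedence. The first point does not explain why distant metastasis alone lacks an interval estimate of the arm difference. The second is a reason to put the correction there, but nothing in the present text commits to it.

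**Conclusion.** The point holds in limited form. One minus Kaplan-Meier, as section 8.5 would produce it, overstates 2-year local and regional failure by 0.5 to 2.1 points at 90% control and by 1.4 to 6.2 points at 70% control. At 30% competing death the excess is 1.6 and 4.5 points. These sizes rest on constant hazards, the assumed range of competing death, and the reading of the quoted control rates as Kaplan-Meier estimates. The direction does not depend on those sizes. The hazard comparison is valid for cause-specific hazards and should be kept.

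The clearer gap is distant metastasis: an objective to compare and a time-to-event label, against a descriptive summary with no between-arm estimate. These are secondary endpoints in a trial not powered for testing, so the correction is worthwhile but not critical.

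**What to change.** In section 8.5, or in the analysis plan before database lock:

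1. Report local, regional and distant failure by arm as cumulative incidence (Aalen-Johansen), measured from randomization, with death without that failure as the competing event. Give the GC4711 minus placebo difference at 12 and 24 months with a 90% confidence interval.
2. Keep the Cox hazard ratio, labelled cause-specific. Use a penalised or profile-likelihood interval if an arm has few or no events.
3. For patients whose imaging stops after another type of progression, censor the cause-specific analysis at the last evaluable imaging, as PFS does. State that this assumes unscanned patients have the same risk as those still scanned.
4. If distant metastasis is also shown as a first-progression event, label it first site of failure. State that it can favour the arm with worse local control and does not recover metastases missed after local failure.

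The cost is wording, routine programming and one more table per endpoint. The data are already collected. The change does not narrow the intervals, and it cannot supply metastases that were never imaged.

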Secondary	
- To determine the degree of in-field tumor response at 6, 12, 18 and 24 months following completion of SBRT- To compare progression-free survival, overall survival, local tumor control, and distant metastasis rates over a 2-year follow up period for SBRT plus GC4711 or placebo- To assess durability of in-field complete or partial responses- To determine acute lung toxicity after SBRT + GC4711 compared to SBRT + placebo for early-stage NSCLC- To evaluate the rate of acute and late radiation toxicities for SBRT + GC4711 compared to SBRT + placebo- To assess the relationship between clinical, functional and radiographical lung function changes observed after SBRT 
- Percent reduction of in-field tumor at Months 6, 12, 18 and 24- Number of participants with CR+PR- Number of participants experiencing grade 1 or higher in diffusion capacity of lung for carbon monoxide (DLCO), measured by RTOG scale, at 6-months after the completion of SBRT- Measurement of the following parameters over 12 months after SBRT
- Changes in pulmonary function testing (pulse oximetry [SpO₂], forced vital capacity [FVC], first expiratory volume in the first second [FEV₁], DLCO), clinical and radiological pneumonitis scoring- Reporting of observed adverse events in patients- Late Radiation Toxicities (including clinical and radiographic pneumonitis, esophagitis, pulmonary fibrosis, rib fractures, plexopathy, cardiac and vascular events) up to 12 months following the completion of SBRT- Measurement of the following parameters over 24 months after SBRT
- Progression Free Survival (PFS)- Overall Survival (OS)- Local and regional control- Distant Metastases (DM) rate

OBJECTIVES	ENDPOINTS
	-

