Clinically, radiation induced pulmonary injury can manifest within weeks to months following radiotherapy. However, most cases are reported within the first 8 months. The classic triad of symptoms includes dyspnea on exertion, non-productive cough, and hypoxemia, though low-grade fevers are also common. Physical exam findings can include pleural friction rub, moist rales as well as signs of consolidation. These manifestations may be complicated by the presence of pre-existing lung disease such as COPD or emphysema. The incidence of symptomatic pneumonitis has dropped with introduction of motion management and other modern RT techniques (Jain 2018). The most used grading system is the Common Terminology Criteria for Adverse Events (CTCAE) published by the National Cancer Institute:

https://ctep.cancer.gov/protocoldevelopment/electronic_applications/docs/ctcae_v5_quick_reference_5x7.pdf

Objectively, the effect of pneumonitis on lung function can be assessed using pulmonary function tests (PFTs), a clinical gold standard. Borst, et al. (2005) reported a decrease in first expiratory volume in 1 s (FEV1) as early as three months post RT; however, most were observed at 6 months. Diffusion capacity of lungs (DLCO) is described as the most prominent PFT

parameter predictive of and impacted by radiation pneumonitis (Stone 2015, Jain 2018). Our primary efficacy measurement of lung function will be prevention of significant falls in DLCO by standard pulmonary function testing. DLCO can be affected by different factors, including alveolar volume and hematologic assessment, as well as smoking, pre-existent chronic obstructive lung disease (COPD), age and medication, including inhalers, oxygen supply and steroids.

In the follow-up portion of this trial, in addition to lung function, hemoglobin will be measured, and medication given for respiratory disease and radiation toxicities (See section 7.4), new anti-cancer treatments will be recorded through 24 months post SBRT completion, as well as smoking and COPD will be monitored throughout 12 months.

PFTs are not part of standard clinical routine follow-up of radiation therapy but can add significant information to radiological and clinical scoring of radiation induced lung injuries. In our study, we measure PFTs every six months in parallel to the radiological assessments (Videtic 2013, Takeda 2013, Ferrero 2015, Vansteenkiste 2014).

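### Lung toxicity is a comparative secondary objective, but Section 8.5 prespecifies no between-arm estimate or interval for DLCO, other lung function tests or pneumonitis

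*Combined protocol and SAP*

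**What the plan says.** Two of the Phase 2 secondary objectives in Section 3 (also in the synopsis) are worded as comparisons with placebo: "To determine acute lung toxicity after SBRT + GC4711 compared to SBRT + placebo for early-stage NSCLC" and "To evaluate the rate of acute and late radiation toxicities for SBRT + GC4711 compared to SBRT + placebo". The endpoints listed with them include a binary one, "Number of participants experiencing grade 1 or higher in diffusion capacity of lung for carbon monoxide (DLCO), measured by RTOG scale, at 6-months", and changes in SpO2, FVC, FEV1, DLCO and pneumonitis scoring over 12 months.

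Section 7.1 Safety Assessments, under Lung function, states: "Our primary efficacy measurement of lung function will be prevention of significant falls in DLCO by standard pulmonary function testing". The same section grades DLCO decline relative to baseline on the RTOG scale, where grade 5 is death.

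Section 8.5 treats the tumour endpoints comparatively. Overall response "will be compared using the same methodology as the primary endpoint", that is, a difference with a two-sided 90% interval plus a descriptive Fisher test. In-field tumour reduction is compared "using a t-test at each timepoint and corresponding two-sided 90% confidence intervals constructed about the difference". PFS, OS and local and regional control get a hazard ratio with a 90% interval.

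For safety endpoints Section 8.5 has one sentence, placed under its Exploratory Endpoints heading: "All safety endpoints will be summarized descriptively including mean and mean change from baseline for continuous endpoints". Categorical ones get counts and percentages. DLCO, PFTs and pneumonitis are not named anywhere in Section 8.5.

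**The concern.** The objective asks how the arms differ, and the analysis text does not say how that difference will be estimated. Reducing radiation lung injury is one of the reasons the protocol gives for running the trial (Synopsis, Rationale and Methodology; Section 4.1). If the comparison is not fixed in advance, the effect measure, the type of interval, the visit and the treatment of deaths and missing tests can all be chosen after data have been seen.

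Timing adds to this. Section 8.7 plans an unblinded efficacy look once the first 20 randomized subjects have 6-month data, and 6 months is also the DLCO time point. Section 8.5 requires the detailed SAP only before database lock. A lung estimator first written down between those two dates would be open to doubt.

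**Working it through.** **1. Objectives against analyses**

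| Phase 2 secondary item (Section 3) | Analysis in Section 8.5 |
|---|---|
| Overall response | Difference, 90% CI, Fisher test |
| In-field tumour reduction | t-test, 90% CI for the difference |
| PFS, OS, local and regional control | Hazard ratio, 90% CI |
| Distant metastases | Descriptive |
| Durability of in-field response | None stated |
| DLCO grade 1 or higher at Month 6, PFT changes, pneumonitis, late toxicity | Not named; at most the descriptive safety sentence |

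That the safety sentence covers DLCO is an inference from lung function being placed under Safety Assessments. If it does not, DLCO has no planned analysis.

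**2. Reproduce the protocol's figure.** Sections 8.1 and 8.5 use half-width = 1.645 × √[p1(1−p1)/n + p2(1−p2)/m]. With p1 = p2 = 0.5 and n = m = 30: 1.645 × √(0.5/30) = 21.2 points, as stated.

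**3. Same formula for DLCO grade 1 or higher.** Section 2.1 gives a rate of 20-30%, about 25%, after SBRT. With equal rates in both arms and 30 per arm:
- 20%: 1.645 × √(2 × 0.20 × 0.80/30) = 17.0 points
- 25%: 1.645 × √(2 × 0.25 × 0.75/30) = 18.4 points
- 30%: 1.645 × √(2 × 0.30 × 0.70/30) = 19.5 points

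Section 8.1 counts drop-out only to 90 days, while DLCO is read at Month 6, so fewer than 30 per arm may have a value. With 24 per arm (an assumption) the half-widths are 19.0, 20.6 and 21.8 points.

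**4. What such an interval could show.** The documents give no target effect. Assume the rate is halved, with 30 per arm. The reduction is placebo minus GC4711, and approximate power is at two-sided 0.10:

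| Placebo vs GC4711 | Reduction (points) | 90% CI | Power |
|---|---|---|---|
| 20% vs 10% | 10.0 | −5.0 to 25.0 | 29% |
| 25% vs 12.5% | 12.5 | −3.9 to 28.9 | 34% |
| 30% vs 15% | 15.0 | −2.4 to 32.4 | 40% |

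**5. Pneumonitis.** Section 2.1 puts symptomatic pneumonitis at about 10% at 6 months: 0.10 × 30 = 3 events per arm. The Wald formula is unreliable at such counts, and an arm with no events adds nothing to its variance.

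**6. Baseline adjustment of continuous tests.** With equal variances at both visits and baseline/follow-up correlation r, the variance of the ANCOVA estimate relative to the change-score estimate is (1−r²)/[2(1−r)] = (1+r)/2. The documents give no r. For assumed values:
- r = 0.6: ratio 0.80; interval narrower by 1 − √0.80, about 11%
- r = 0.7: ratio 0.85; narrower by 1 − √0.85, about 8%
- r = 0.8: ratio 0.90; narrower by 1 − √0.90, about 5%

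**The case against.** The best defence is that the trial is openly an estimation study. Section 8.5 says it is not powered for formal tests and that p-values are descriptive, and it announces a more detailed SAP that will supersede the protocol on analytic conventions. If counts are tabulated by arm, any reader can work out a crude difference. The step 4 figures also show that a prespecified interval would probably include zero even if the drug halved the rate.

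Much of this stands, but it limits the size of the point and does not remove it. Estimation by interval width is the trial's declared aim in Section 8.1, so an interval for the lung endpoint fits the design. The announced SAP, which is not in the supplied text, is to elaborate the analyses described in Section 8.5, and no lung comparison is described there.

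Four stronger readings are tempting, and the documents do not support them:
- **Baseline lung function is ignored.** It is used, through mean change and through RTOG grades defined by decline from baseline. What is missing is its use as a covariate.
- **Lung endpoints alone lack an estimate.** Distant metastases are only described, and durability of response has no stated method.
- **No risk-factor analysis is planned.** Section 3 lists an exploratory one for lung function decline and pneumonitis, though Section 8.5 gives it no method.
- **The lung question will go unanswered.** It is under-specified: a crude comparison could still be derived, or added in the later SAP.

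**Conclusion.** The point holds in this limited form: a comparative secondary objective has no prespecified between-arm estimate or interval, and the only text that can apply is descriptive and has no covariate adjustment. It should be corrected, but it does not affect the primary analysis.

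Precision for DLCO decline would be about 17.0-19.5 points at 30 per arm. That is no wider than the 21.2 points accepted for the primary endpoint, although 21.2 is the worst case over all response rates. The range assumes that the cited 20-30% rate applies to this population, which may also receive 3 fractions, and that 30 per arm have Month 6 tests; at 24 per arm it reaches 19.0-21.8. The gain is a prespecified estimate, not a decisive answer. The 10-20% variance reduction from ANCOVA rests wholly on the assumed correlations of 0.8-0.6 and is a refinement.

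**What to change.** In the secondary analyses of Section 8.5:

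1. Name DLCO grade 1 or higher at Month 6 as the lead lung endpoint. Report the GC4711-minus-placebo difference with a two-sided 90% score-type interval.
2. Report the same for clinical pneumonitis. The score-type interval matters most here because few events are expected.
3. State the denominator for both, how deaths count (grade 5 on the RTOG scale) and how patients without a Month 6 PFT are handled.
4. Analyse continuous DLCO, FEV1, FVC and SpO2 at Months 6 and 12 by ANCOVA with the baseline value as covariate and a 90% interval, labelled supportive. ANCOVA does not apply to the binary lead endpoint.
5. Settle this text before the unblinded interim look in Section 8.7.

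The cost is a few lines of text. All the data are already scheduled (PFTs at screening, Month 6 and Month 12), so no patients or visits are added. Item 4 adds 4 measures × 2 visits = 8 descriptive intervals, which is why one lead endpoint should be named.
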